## **Analysis of Primary Effectiveness Outcome**

The primary effectiveness outcome will be analyzed with intent-to-treat (ITT) approach by including all randomized patients regardless of crossover or drop-out. The change in total atheroma volume within a  $\geq 20$  mm long segment of the target coronary artery from baseline to 90-day follow-up will be analyzed using the two-sample t-test. We will define their change scores to be 0 if they do not have an atheroma volume measurement at 90-day follow-up. Analysis of Covariance (ANCOVA) will be performed to evaluate the treatment effect on primary effectiveness outcome adjusting for age, pre-existing CAD, pre-existing diabetes, and baseline LDL levels.

## **Analysis of Secondary Effectiveness Outcomes**

The intent-to-treat principle will also be applied to all the secondary effectiveness outcomes analyses.

The change of %NC component of atheroma from baseline to 90-day follow-up will be analyzed using the two-sample t-test. The change scores for those who miss the 90-day follow-up assessment will be set to zero. Analysis of Covariance (ANCOVA) will be performed to evaluate the treatment effect on primary effectiveness outcome adjusting for age, pre-existing CAD, pre-existing diabetes, and baseline LDL levels.

The EPC-CFU/ml of peripheral blood assessed at 4 time points (pre-PCI, post-PCI, 30-day follow-up, and 90-day follow-up) will be analyzed via Mixed Linear models with random intercepts. The treatment effect, time effect and their interaction will be considered with or without adjusting for age, pre-existing CAD, pre-existing diabetes, baseline LDL levels, and other relevant covariates such as ACS, peripheral vascular disease, and chronic kidney disease. The statistical test of interest is the time by treatment interaction. Contrasts will be used in the Mixed Linear models to compare the differences among any specifically interested time points.

The incidence of major adverse cardiovascular endpoints (MACE) including death, myocardial infarction, coronary revascularization, and stroke will be analyzed in two ways. The percentage of people who experience the event at least once will be compared using the chi-square test. Logistic regression models will be performed to adjust for the covariates such as age, pre-existing CAD and pre-existing diabetes. An event-based analysis will also be done since MACE can be recurrent. In this analysis, a non-parametric method called the mean cumulative function (MCF) will be used as an alternative to the above crude incidence rate analyses. The overall safety profiles as well as the safety profiles in specific subgroups over the whole study period will be compared for the two randomization groups including the times of event recurrence and censoring mechanisms. Time to event (survival analysis) will also compare the time to first MACE between treatment groups. A second survival analysis will be performed to identify risk predictors and to evaluate whether the observed treatment effect is modified by adjusting for covariates such as pre-existing CAD and pre-existing diabetes.

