This is the second phase of a multi-center trial of ACS patients. The first phase was a safety study involving 31 patients and was completed in December 2012. US Food and Drug Administration (FDA) reviewed the safety and efficacy data from the first phase and approved proceeding to this phase. In this trial, 128 participants will be randomized in a 1:1 ratio to either initial LDL-apheresis and an oral daily dose of 40-80mg of Atorvastatin or equivalent (ILLT group) vs. a daily dose of 40-80mg of Atorvastatin or equivalent without LDL-apheresis (SMT group) following an uncomplicated PCI. Intravascular ultrasound with virtual histology (IVUS-VH) derived coronary atheroma volume and composition will be obtained at baseline and 90 days after enrollment, while peripheral blood sampling will be performed at enrollment, and at 24 hours, 30 days, and 90 days post-PCI, along with a four-month and a six-month clinical follow-up visits to determine whether the ILLT group will affect:

1. The total number of and percentage of patients with major peri-PCI procedure adverse events (primary safety endpoint)

2. The total number of and percentage of patients with statin-related abnormal liver function test events and statin-related muscle injury events (secondary safety endpoint)
3. The total atheroma volume within a ≥ 20 mm long segment of the target coronary artery at 90 days IVUS-VH follow-up (primary effectiveness endpoint)
4. The %NC component within a ≥ 20 mm long segment of the target coronary artery at 90 days IVUS-VH follow-up (secondary effectiveness endpoint)
5. The EPC-CFU/ml of peripheral blood, compared to SMT group from baseline to 30 days and 90 days post-PCI (secondary effectiveness endpoint)
6. The major adverse CV events (MACE) at 90 days and at six months follow-up (secondary effectiveness endpoint)

2. Background and Significance

2(a) Background

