Peripheral blood sampling for EPC quantification will be performed using cell culture only at VA North Texas center in Dallas. This will ensure an optimal number (at least 50) uniformly standardized and cost-effective EPC cell culture assays in this multi-center study. A limited number (n=25) of FACS EPC analysis will be performed to correlate cell culture and FACS levels of circulating EPC. Such a correlation would be important to demonstrate if future large-scale use of this treatment strategy of EPC mobilization is to be implemented with the rapid and less cumbersome FACS instead of the established standard of EPC cell culture technique. Approximately 10ml of whole blood is needed for either assay. Cell culture assay based upon our published methodology¹¹ will be performed ≤ 48 hours of collection. EPC flow cytometry will be performed using standard methodology³⁴. All EPC sampling schedules are indicated in **Figure 8** and in **Table 1**, along with all other scheduled clinical and laboratory tests. All EPC analyses will be compared to baseline pre-PCI levels. **Table 1** summarizes all planned follow-up visits and tests.

Follow-up tests like fasting lipid (FL) will be performed immediately following LDL-apheresis in ILLT device group at about 12-24 hours post-PCI procedure. The same fasting lipid profile test for SMT control group will be done at 24 hours post-PCI procedure or prior to hospital discharge, whichever comes earlier. A post-PCI 30-day visit will include a complete blood count (CBC) and basic metabolic profile (BMP) with LFT. The 30-day post-PCI CBC, BMP and LFT are clinically indicated tests. A 30- and 90-day FL in both treatment groups, along with EPC assay and an additional 60 day phone follow-up, will ensure strict lipid management and close follow-up for clinical

events, and prevent any loss of recruited study subjects. After the 90-day follow-up cardiac catheterization and IVUS-VH analysis, all study subjects will return in 30 days for a 4-month study visit with CBC, BMP, LFT and FL. After an additional 60 days, or at 6 months from index PCI, all patients will return for a study completion visit and a FL assay. Any MACE will also be collected via searching the Austin database of VA hospital utilization by Hines CSPCC staff. This dual MACE assessment will help avoid missing out on any participating site MACE.

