4(g)(ix). Sensitivity Analysis for Missing Data: In addition to the above mentioned ITT principle for primary and secondary effectiveness outcomes in which the change scores will be set to zero if the follow-up assessment is missing, other approaches will be applied in order to assess the robustness of the study results to assumptions about the missing data. For outcomes about atheroma volume and % of NC component of atheroma which will be measured only at 2 time points, the sensitivity analysis approaches include: 1) performing analysis only on complete data, 2) applying the worst case scenario (set the lowest score at baseline and the highest score at 90-day), and 3) generating imputes for missing data with multiple imputation. For outcome about EPC-CFU/ml of peripheral blood which will be repeatedly measured at four time points, the sensitivity analysis approaches include: 1) performing analysis only on complete data, and 2) using the mixed model for repeated measures.

All tests will be two-sided. The critical level for all the primary and secondary outcomes will be 0.05. No adjustments will be made for multiple secondary endpoints.

4(h) Quality Assurance, Oversight and Study Regulation

4(h)(i) Training to assure accuracy, precision and validity of the data: Toward the end of the six-month start-up period, training of study personnel will take place during a two-day kick-off meeting. All participating investigators, site research coordinators/raters, and Hines CSPCC personnel will be in attendance. Prior to the meeting, case report forms will be finalized and a detailed manual of study operations will be written and circulated. This manual will serve as the training manual for the meeting and as a reference document following the meeting. The PI's office and the data and pharmacy coordinating centers will provide the training. The general training will include the study treatment, patient screening and consent, baseline evaluation, follow-up procedures, and proper entry and maintenance of data. Cyber security awareness training and privacy training (VHA Privacy Policy, Protection of Human Research Subjects, and Good Clinical Practices) are required annually of all VA and VA-WOC employees.

4(h)(ii). Data Management and Security

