## **Handling Missing Data**

The Intent-to-treat (ITT) principle will be applied for primary and secondary effectiveness outcomes in which the change scores will be set to zero if the follow-up assessment is missing.

Other approaches will also be applied in order to assess the robustness of the study results for assumptions about the missing data. For outcomes about atheroma volume and % of NC component of atheroma which will be measured only at 2 time points, the sensitivity analysis approaches include: 1) performing analysis only on complete data, 2) applying the worst case scenario (set the lowest score at baseline and the highest score at 90-day follow-up), and 3) generating imputes for missing data with multiple imputation. For outcome about EPC-CFU/ml of peripheral blood which will be repeatedly measured at 4 time points, the sensitivity analysis approaches include: 1) performing analysis only on complete data, and 2) using the mixed model for repeated measures.

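### The EPC model has only a random intercept for samples at 0, 1, 30 and 90 days, so its visit-specific standard errors can be wrong in a direction the documents cannot settle; use an unstructured covariance

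*SAP*

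**What the plan says.** - **Model.** SAP, Analysis of Secondary Effectiveness Outcomes, says that EPC-CFU/ml "will be analyzed via Mixed Linear models with random intercepts". Protocol 4(g)(v)(2) says the same. Neither names a residual structure, random slope, robust standard error or degrees-of-freedom method.
- **Sampling times.** Protocol 1(c): "peripheral blood sampling will be performed at enrollment, and at 24 hours, 30 days, and 90 days post-PCI". The gaps between successive samples are therefore about 1, 29 and 60 days.
- **Tests.** "The statistical test of interest is the time by treatment interaction". In addition, "Contrasts will be used in the Mixed Linear models to compare the differences among any specifically interested time points". Protocol 1(c) states the EPC objective as the change from baseline to 30 and 90 days, and Protocol 4(e) adds: "All EPC analyses will be compared to baseline pre-PCI levels".
- **Sensitivity analysis.** SAP, Handling Missing Data, and Protocol 4(g)(ix) list for EPC an analysis of complete data and one "using the mixed model for repeated measures". No covariance structure is given for the latter.
- **Size and level.** EPC culture is done at Dallas only: "This will ensure an optimal number (at least 50) uniformly standardized and cost-effective EPC cell culture assays" (Protocol 4(e)). Protocol 4(g)(ix): "The critical level for all the primary and secondary outcomes will be 0.05", two-sided.

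**The concern.** A random intercept with independent residuals implies compound symmetry: equal variance at all four visits and equal correlation between any two of them. Every change from baseline then gets the same model standard error, built from a residual pooled over all visits.

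This schedule gives two reasons to doubt that. Two samples a day apart may correlate more closely than two samples 90 days apart. Also, PCI, and in one arm apheresis, falls between the first and second samples, so the 24-hour value may have its own variance or its own correlation with the rest. Either would break the assumption.

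The contrasts at 30 and 90 days, which carry the stated objective, would then not be tested at their nominal 5% level. The model free of this restriction, if fitted with an unstructured covariance, appears only as a missing-data sensitivity analysis.

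**Working it through.** **Figures in the plan.** There is none to reproduce for EPC: the documents give no standard deviation by visit, between-visit correlation, effect size or power. The one sample-size figure, 128, belongs to atheroma volume. It reproduces (51 per arm for d = 0.65 at 90% power; 102/0.80 = 127.5) but has no bearing on the EPC model.

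**Inputs.** Four visits, alpha 0.05 two-sided and 1:1 allocation come from the documents. Assumed: categorical time (a 3-df interaction), complete data, independent residuals, and every variance and correlation below. For sample size I used 25 per arm (reading the Dallas figure as 50 patients) and 16 per arm (128/4 sites = 32, halved). Standard-error ratios do not depend on this choice.

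**Formula.** With V for variance and C for covariance, for the change from baseline (0) to visit j:

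model SE / true SE = sqrt[ 2(mean variance − mean covariance) / (V0 + Vj − 2·C0j) ]

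**Worked case, decaying correlation and equal variances.** Baseline correlates 0.8, 0.5 and 0.4 with 24 hours, 30 days and 90 days; the other pairs are 0.5 (24 h–30 d), 0.4 (24 h–90 d) and 0.6 (30 d–90 d). The mean correlation is 3.2/6 = 0.533, so 1 − 0.533 = 0.467.

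- 24 hours: sqrt(0.467/0.2) = 1.53
- 30 days: sqrt(0.467/0.5) = 0.97
- 90 days: sqrt(0.467/0.6) = 0.88

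A large-sample check at 90 days: the critical value is effectively 1.96 × 0.88 = 1.73, a two-sided tail of about 8%.

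**Same correlations, 24-hour SD 1.5 times the others.** Mean variance is 5.25/4 = 1.3125. Covariances sum to 1.2 + 0.5 + 0.4 + 0.75 + 0.6 + 0.6 = 4.05, mean 0.675. Twice the difference is 1.275. The true variances of change are 0.85, 1.00 and 1.20, so the ratios are 1.22, 1.13 and 1.03. The 90-day standard error is no longer too small.

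**Simulated type I error** (20,000 null trials per pattern, 25 per arm; results at 16 per arm agree to within about 0.2 percentage points):

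| Assumed pattern | SE ratio 24 h / 30 d / 90 d | Type I error 24 h / 30 d / 90 d | Interaction |
|---|---|---|---|
| Baseline 0.7/0.5/0.45, other pairs 0.5/0.45/0.55 | 1.26 / 0.98 / 0.93 | 1.6% / 5.6% / 7.0% | 5.5% |
| Baseline 0.8/0.5/0.4, other pairs 0.5/0.4/0.6 | 1.53 / 0.97 / 0.88 | 0.3% / 5.9% / 8.5% | 6.3% |
| Baseline 0.9/0.4/0.3, other pairs 0.4/0.3/0.5 | 2.31 / 0.94 / 0.87 | 0% / 6.6% / 8.8% | 7.1% |
| All correlations 0.5, equal SDs | 1.00 / 1.00 / 1.00 | about 5% throughout | about 5% |
| Second row, 24-hour SD 1.5 | 1.22 / 1.13 / 1.03 | 1.7% / 2.7% / 4.5% | 6.6% |
| All correlations 0.5, 24-hour SD 1.5 | 0.89 / 1.17 / 1.17 | 8.4% / 2.1% / 2.3% | 5.7% |
| 24-hour correlation 0.2 with all, others 0.5 | 0.90 / 1.14 / 1.14 | 7.6% / 2.6% / 2.6% | 5.5% |

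Other choices for the later-visit correlations, with the same three sets of baseline correlations, moved the 90-day figure between 6.6% and 9.4%. Seven smooth-decay covariances with equal variances gave 6.7% to 13.6% at 90 days. The top of that range needs a 24-hour correlation near 1. Across those seven, the 30-day ratio ran from 0.94 to 1.23, on both sides of 1.

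**With the proposed change.** Contrasts that use each visit's own variance of change, equivalent to an unstructured covariance when data are complete, stayed at about 5% in every pattern above, including the reversals.

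**The case against.** The strongest reply is that the direction is unknown. A reader might infer that the standard errors are definitely too small at 90 days and too large at 24 hours. The documents do not support that: it needs correlation that falls with the gap and also equal variances, and they give figures for neither. The 24-hour sample is not a neutral repeat. Protocol 3(a) reports that EPC levels rose after PCI in elective patients (P = 0.0009), though not in ACS patients (P = 0.20), so extra spread at that visit is plausible but not shown. A reader might also infer that the 30-day contrast is badly inflated. In the decaying patterns in the table it is only slightly so, and under some smooth-decay patterns it is conservative. These objections stand, and they limit the claim.

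It can also be said that the named test is the interaction, where the error is small; that the contrasts are not tied to particular visits; and that a repeated-measures model is already prespecified for EPC. The first is true. On the second, the 30- and 90-day objective makes those visits the natural contrasts. On the third, that model could expose the problem, but it is only a sensitivity analysis and names no covariance structure, so the gap in the primary model remains.

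Finally, the impact is bounded: one secondary endpoint at one site, and with complete data only standard errors and p-values change. That stands too.

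**Conclusion.** The concern holds in a limited form. The planned EPC model imposes one variance and one correlation on four unequally spaced visits, with procedures between the first two. If that is wrong, the visit-specific standard errors and p-values are wrong.

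Under decaying correlation and equal variances, both assumed, type I error is about 6.5–9% for the 90-day contrast, 5.5–6.5% at 30 days, 0–1.5% at 24 hours and 5–7.5% for the interaction. A more variable 24-hour sample removes the 90-day inflation or reverses the direction. If correlation and variance really are equal across visits, there is no error. All of these figures rest on assumed covariances, complete data, categorical time and independent residuals.

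The case for changing the model does not depend on the direction, because the unstructured model held about 5% whichever way the error ran.

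**What to change.** In SAP, Analysis of Secondary Effectiveness Outcomes, and Protocol 4(g)(v)(2), make the primary EPC analysis a repeated-measures mixed model with visit as a category, treatment, their interaction, an unstructured covariance and Kenward-Roger degrees of freedom. Prespecify a fallback if it does not converge: a simpler structure with robust standard errors.

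The random-intercept model can stay as a sensitivity analysis. In SAP, Handling Missing Data, and Protocol 4(g)(ix), stop counting the repeated-measures model as a test of the missing-data assumption. It would now be the primary analysis, and both mixed models rely on data being missing at random. A reader might conclude that it should simply be deleted from that list, but this would leave only the complete-data analysis for EPC. The team should decide what takes its place.

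The cost is SAP and protocol wording and one covariance option in the code. The downside is more covariance parameters at the Dallas sample size: 4 × 5/2 = 10, against 2 for the random intercept. Kenward-Roger and the fallback are there to handle that.

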ACS is defined as chest discomfort lasting at least 10 min within the last 24h, new ≥ 1 mm ST-wave or dynamic T-wave changes in at least two contiguous EKG leads but without significant ST elevation, and/or troponin I or T levels above the 99th percentile. Abnormal LFT is defined as any liver transaminases (ALT or AST) ≥ 3 times the upper limit of the normal laboratory reference. Atorvastatin 40-80mg will be considered equivalent to 20-40mg of Rosuvastatin. Patients on Simvastatin at the time of enrollment will be switched to Atorvastatin 40-80 mg or Rosuvastatin 20-40 mg.

After PCI of the target or culprit coronary artery (as determined by the operator) and IVUS-VH analysis of a ≥ 20 mm segment of the target coronary artery are performed during the index hospitalization for the qualifying ACS event, the patients will be randomized to ILLT or SMT if they meet all inclusion and exclusion criteria (**Figure 7, blue arrow**). PCI will be performed using standard technique at the discretion of the operator. 40-80mg daily Atorvastatin or equivalent treatments (ILLT or SMT) will be initiated within 24 hours after randomization. Patients randomized to the ILLT arm will undergo LDL-apheresis within 36 hours after presentation unless the 36-hour window is mandatory for those who were on ACE inhibitors to allow for the complete washout of ACE inhibitors. Adjunctive anti-platelet and anti-thrombin therapies will be at the discretion of the primary operator and clinical team. Refer to **Figure 8** for all study timelines.

4(c)(ii). Inclusion Criteria:

- (1). Willing and able to provide informed consent (including HIPAA)
- (2). Age > 30 years

- (3). Presenting with acute coronary syndrome (ACS), manifested as unstable angina or non-ST-elevation myocardial infarction
- (4). Referred for clinically indicated, non-emergent (the procedure is not required to be performed within 3 hours after patient presentation) coronary angiography and PCI with IVUS-VH of target coronary artery for ACS
- (5). Successful placement of two large-bore IV cannulas in bilateral upper extremities
- (6). Fasting (≥ 12 hrs) LDL ≥ 70 mg/dl while on ≤ 80 mg Atorvastatin or equivalent dose of other statin, performed at time of admission

4(c)(iii). Exclusion Criteria:

- (1). Known allergy to aspirin, statins, or iodinated contrast
- (2). Positive pregnancy test, planning to become pregnant, or breast-feeding

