- (2). The EPC-CFU/ml of peripheral blood assessed at various time points (pre-PCI, post-PCI, 30 days of follow-up, and 90 days of follow-up) will be analyzed via Mixed Linear models with random intercepts. The treatment effect, time effect and their interaction will be considered with or without

adjusting for age, pre-existing CAD, pre-existing diabetes, baseline LDL levels, and other relevant covariates such as ACS, peripheral vascular disease, and chronic kidney disease. The statistical test of interest is the time by treatment interaction.

- (3). Contrasts will be used in the Mixed Linear models to compare the differences among any specifically interested time points.

4(g)(vi). Statistical Analysis of Safety Endpoints and Complications: The primary safety endpoints, the secondary safety endpoints, and the incidence of major adverse cardiovascular endpoints (MACE) including death, myocardial infarction, coronary revascularization, and stroke will be analyzed in two ways. For each type of event, the percentage of people who experience the event at least once will be compared using the chi-square test. Logistic regression models will be performed to adjust for the covariates such as age, pre-existing CAD, and pre-existing diabetes. In addition, a similar analysis will be done for all AE and SAE that are possibly or probably attributable to the study intervention.

An event-based analysis will also be done since adverse events can be recurrent. In this analysis, a non-parametric method called the mean cumulative function (MCF)^{35,36} will be used as an alternative to the above crude incidence rate analyses. The overall safety profiles as well as the safety profiles in specific subgroups over the whole study period will be compared for the two randomization groups including the times of event recurrence and censoring mechanisms.

Time to event (survival analysis) will also compare the time to first MACE between treatment groups. A second survival analysis will be performed to identify risk predictors and to evaluate whether the observed treatment effect is modified by adjusting for covariates such as pre-existing CAD and pre-existing diabetes.

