## **Secondary Effectiveness Outcome Measures**

The secondary effectiveness outcome measures will include:

1. The %NC component of atheroma. The %NC component of atheroma will be obtained via IVUS-VH at 2 time points (baseline during index PCI and 90-day follow-up).
2. EPC-CFU/ml of peripheral blood. The cell culture assay and quantification of circulating EPC-CFU will be performed for patients recruited at the Dallas VA center only. The assay will be done at 4 time points (pre-PCI, post-PCI, 30-day follow-up, and 90-day follow-up).

3. The major adverse cardiovascular endpoints (MACE) including death, myocardial infarction, coronary revascularization, and stroke during the follow-up periods. The major adverse CV events will be collected via both clinical visits for up to 6 months post-PCI and searches of the VA Austin database for up to 1 year post-PCI. Approvals for using the patients' Social Security Numbers for data searching will be obtained via informed consent form.

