### **Sample Size Determination**

There is only one study which examined the treatment of medication only (20mg Pravastatin or 10mg Simvastatin) vs. LDL-apheresis with statin medication on coronary plaque regression in familial hypercholesterolemia and published in 2002 Journal of American College of Cardiology. The trial reported the net change of plaque area from baseline to one year follow-up. The changes were  $-0.69 \pm 2.08 \text{mm}^2$  in the LDL-apheresis group vs.  $0.88 \pm 1.75 \text{mm}^2$  in the medication only group. Two studies, which have primarily mobilized coronary atheroma LDL using HDL or its apoprotein, have shown similar magnitude of atheroma regression at 6-10 weeks, without directly lowering LDL levels. Given the expected 85% reduction in LDL after LDL-apheresis, we expect to observe a similar treatment effect for the primary effectiveness outcome of this study at 12 weeks.

The sample size of 30 patients for the first feasibility/pilot study leads to a power of 54% with  $\alpha = 0.05$  and the same effect size as reported in the published paper (Cohen's D effect size = 0.82 for  $-0.69 \pm 2.08 \text{mm}^2$  in the LDL-A group vs.  $0.88 \pm 1.75 \text{mm}^2$  in the medication only group). The power decreases to 38% with  $\alpha = 0.05$  and a more meaningful lower Cohen's D effect size of 0.65 by decreasing the difference of two treatment means by 20% ( $-0.38 \pm 2.08 \text{mm}^2$  in the LDL-A group vs.  $0.88 \pm 1.75 \text{mm}^2$  in the medication only group). The power decreases further to 31% by considering 20% drop-out rate with  $\alpha = 0.05$  and the Cohen's D effect size = 0.65.

The second stage of pivotal study is approved to obtain the 90% power to detect a Cohen's D effect size of 0.65 ( $-0.38 \pm 2.08 \text{mm}^2$  in the LDL-A group vs.  $0.88 \pm 1.75 \text{mm}^2$  in the medication only group) with the randomization scheme of 1:1,  $\alpha = 0.05$ , and a 20% drop-out rate, the pivotal study needs a sample size of 128.

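### Entered as main effects, the EPC-CFU/ml covariates cancel from the time-by-treatment test; adjusting for the pre-PCI EPC value would sharpen the comparison

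*SAP*

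**What the plan says.** The SAP (Analysis of Secondary Effectiveness Outcomes) states that EPC-CFU/ml "will be analyzed via Mixed Linear models with random intercepts" and names a single test: "The statistical test of interest is the time by treatment interaction". The samples are set out under Secondary Effectiveness Outcome Measures: "The assay will be done at 4 time points (pre-PCI, post-PCI, 30-day follow-up, and 90-day follow-up".

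The covariate clause reads "The treatment effect, time effect and their interaction will be considered with or without adjusting for age, pre-existing CAD, pre-existing diabetes, baseline LDL levels" and continues with "other relevant covariates such as ACS, peripheral vascular disease, and chronic kidney disease". Protocol 4(g)(v)(2) says the same. No covariate is described as updated over time. Neither document says whether the covariates enter alone or crossed with time, or which of the two versions is the main one. The pre-PCI EPC value appears only as the first of the four outcomes.

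Two further passages bear on the point. Inclusion criterion (3) in Protocol 4(c)(ii) requires ACS of every patient: "Presenting with acute coronary syndrome (ACS), manifested as unstable angina or non-ST-elevation myocardial infarction". Protocol 4(e) limits the culture assay to Dallas and says of that choice: "This will ensure an optimal number (at least 50) uniformly standardized and cost-effective EPC cell culture assays in this multi-center study".

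**The concern.** The covariates are characteristics of the patient, fixed at baseline. The time-by-treatment interaction compares changes within patients. A fixed characteristic entered as a main effect moves all of a patient's values by the same amount, so it leaves those changes untouched. The adjusted analysis would then repeat the unadjusted one for the only test named, and a reader could take their agreement as evidence that covariate imbalance does not matter.

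Precision is also at stake. EPC is measured at one site. At 1.5 patients per month for 22 months (Protocol 4(g)(iii)) Dallas would contribute about 33 patients; Protocol 4(e) speaks of at least 50 assays. With either number, the covariate most closely tied to the outcome, the patient's own pre-PCI value, is not used as a covariate.

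**Working it through.** The documents give no effect size, SD or power for EPC, so there is no planned figure to reproduce.

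**1. Algebra.** For patient *i* at visit *t* (0 = pre-PCI), with arm *A* and fixed covariates *Z* as main effects:

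Y_it = a + b_t + g·A_i + d_t·A_i + c·Z_i + u_i + e_it, with d_0 = 0.

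The change from baseline is Y_it − Y_i0 = (b_t − b_0) + d_t·A_i + (e_it − e_i0). The terms g·A_i, c·Z_i and u_i have gone. With all four samples present, the estimate of d_t is the difference between arms in mean change, whatever *Z* contains.

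**2. Complete data.**
- 33 patients × 4 visits, five covariates: the last interaction term is 1.15691 (SE 0.47419) both unadjusted and adjusted.
- 50 patients (25 per arm), seven covariates, assumed intraclass correlation 0.5: the interaction F statistics differ by less than 1e-6, the SE ratio is 1.0000 and no conclusion differs.
- With a fixed unstructured covariance the estimates and SEs are again identical.

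**3. Missing follow-up.** The trial allows for drop-out: "and a 20% drop-out rate, the pivotal study needs a sample size of 128". Same 50-patient set-up, main effects, 1,000 simulated trials per row:

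| Missingness | SE ratio, 90-day term | Median (maximum) p-value shift | Significance differs | Rejection rate, unadjusted → adjusted |
|---|---|---|---|---|
| 20%, completely at random | 0.994 | 0.006 (0.20) | 4.5% | 47.3% → 48.2% |
| 20%, at random | 0.994 | 0.006 (0.18) | 4.0% | 47.6% → 48.6% |
| 20%, at random, stronger covariates | 0.992 | 0.007 (0.17) | 4.9% | 51.0% → 52.5% |
| 40%, at random, stronger covariates | 0.984 | 0.016 (0.29) | 6.4% | 39.5% → 40.3% |

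A smaller run (400 trials, 20% completely at random) gave 2.8% differing. The identity becomes exact again in the planned complete-data sensitivity analysis, if that keeps only patients with all four samples. It would also be exact if the zero-change rule were used to fill missing EPC values; the SAP does not say whether that rule reaches the mixed model.

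**4. Where the adjustment does act.** In the complete-data fits of step 2 the SE of the treatment main-effect term fell by about 27%. That term is a between-patient comparison and not the test of interest.

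**5. Pre-PCI EPC as covariate.** The pre-PCI sample precedes randomization, which follows PCI (Protocol 4(c)(i), 4(c)(v)(2), Table 1), so it is a valid baseline covariate. With equal variance σ² and within-patient correlation ρ, and up to the same factor for group sizes:
- change from baseline: 2σ²(1 − ρ)
- baseline-adjusted: σ²(1 − ρ²)
- ratio: (1 − ρ²) / [2(1 − ρ)] = (1 + ρ)/2

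For ρ = 0.3, 0.5 and 0.7 the ratio is 0.65, 0.75 and 0.85, a cut of 35%, 25% and 15%. In simulation the cuts were about 33%, 22% and 12% with 33 patients, and about 34%, 23% and 14% with 50.

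The joint test over the three post-baseline visits gains too. The covariance of the three contrasts is proportional to (1 − ρ)(I + J) for changes and (1 − ρ)(I + ρJ) after adjustment, where J is the matrix of ones. Since ρ < 1, the adjusted test has at least as large a noncentrality for any pattern of effects. For an effect equal at all three visits it is 3/(1 + 3ρ) against 3/4; at ρ = 0.5 that is 1.20 against 0.75.

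**6. Which test.** Once only post-baseline values are modelled, treatment × visit asks whether the effect differs between visits. Against a constant effect its power is 5%, the significance level itself.

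**The case against.** **The form of adjustment is open.** A reader might infer that the plan cannot adjust its own test, or that it reports one test twice. The documents do not support that as fact, because they do not exclude covariate-by-time terms. Such terms do change the test: with seven covariates in 50 patients and a true effect, the conclusion at 0.05 differed in 14% of simulated trials and the 90-day SE rose by about 8%. This objection stands. The point is conditional on main effects, which is the natural reading because the only interaction the plan names is treatment with time.

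**The two versions need not agree.** A reader might infer that they always will. With missing samples they do not, as step 3 of the working shows. Near-identity is the right description.

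**No robustness claim is made.** Neither document calls the adjusted EPC model a robustness check; the SAP (Handling Missing Data) names complete-data analysis and a mixed model for repeated measures as the EPC sensitivity analyses. That stands. What remains is a limit on what agreement between the two versions could show.

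**The planned test is valid.** The within-patient contrast already removes additive imbalance in these covariates, and keeping baseline among the outcomes is legitimate. Also true: the loss is precision, not validity.

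**ACS is probably shorthand.** A reader might call this covariate an error because every patient has ACS. Protocol 4(g)(viii) splits ACS into unstable angina and non-ST-elevation MI, so the type of ACS is plausibly meant, and a constant covariate would drop out harmlessly. It needs only clearer wording.

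**Conclusion.** The point holds in conditional form. If the listed covariates enter as main effects, they do nothing to the named EPC test with complete data and almost nothing with about 20% missing follow-up. Agreement between the adjusted and unadjusted interaction tests is therefore built in and uninformative about covariates. There is no bias, no inflation of type I error and no effect on the primary analysis; the endpoint is secondary and comes from one site.

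The avoidable loss is precision: about 15–35% of the variance of a visit contrast for an assumed correlation of 0.7 down to 0.3, slightly less in small samples. The complete-data identity needs no assumption beyond main effects. The missing-data figures rest on assumed intraclass correlation, covariate strength, effect size and missingness; the precision figures rest on the assumed correlation and equal variances across visits.

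**What to change.** In SAP, Analysis of Secondary Effectiveness Outcomes, and Protocol 4(g)(v)(2):

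1. Make the main EPC analysis a model of the post-PCI, 30-day and 90-day values, with treatment × visit and pre-PCI EPC × visit.
2. Replace the sentence naming the test of interest. Use either the baseline-adjusted treatment difference at 30 and 90 days, the visits named in the EPC objective of Protocol 1(c), or the joint test of treatment over all post-baseline visits. Do not keep the treatment × visit interaction alone.
3. Name this as the main version. In one supportive model, add a short fixed list of the covariates as main effects. Here they do act, because the visit-specific treatment difference compares patients with patients.
4. Replace ACS in the list by ACS type, unstable angina versus non-ST-elevation MI.

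The cost is wording in both documents and a few degrees of freedom. No new data are needed. The list should stay short: crossing five covariates with visit in the 33-patient example raised the SE from 0.474 to 0.539, about 14%.
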